### **8.3.2 Analysis of EQ-Visual Analogue Scale (VAS)**

Descriptive analysis for actual and change from baseline scores for VAS will be provided by study part, dose level and visit.

The one sample Wilcoxon signed rank test for a single group will be used to compare the baseline VAS result vs the last post-baseline assessment at the final treatment dose VAS result, independently for each dose level in Part 2. A 95% Confidence interval for the median change from baseline value at the last post-baseline assessment at the final treatment dose will also be obtained. Sample SAS code can be found in Appendix I.

### **8.3.3 Analysis of Hemophilia A quality of life questionnaire (Haem-A-QoL)**

Haem-A-QoL comprises of 10 scales and one total Haem-A-QOL transformed score (HAEMA\_Z):

- Physical health (PHYS) - 5 items
- Feelings (FEEL) - 4 items
- View of yourself (VIEW) - 5 items
- Sports and Leisure (SPORT) - 5 items
- Work and school (WORK) - 4 items
- Dealing with Haemophilia (DEAL) - 3 items
- Treatment (TREAT) - 8 items
- Future (FUTURE) - 5 items
- Family planning (FAMPL) - 4 items
- Partnership and sexuality (SEXUAL) - 3 items

Statistical Analysis Plan

Catalyst Biosciences, Inc. Protocol # MAA-201

Version 2.0

Syneos Health #1009647

For the detailed scoring method, please see [Appendix III](#).

Descriptive analyses for the actual and change from baseline scores for Haem-A-QoL will be provided for each of the dimensions by study part, dose level and visit.

The one sample Wilcoxon signed rank test for a single group will be used to compare the baseline Haem-A-QoL result vs. the last post-baseline assessment at the final treatment dose Haem-A-QoL result per subject, independently for each dose level in Part 2. A 95% Confidence interval for the median change from baseline value at the last post-baseline assessment at the final treatment dose will also be obtained. Sample SAS code can be found in Appendix I.

### 8.3.4 Analysis of Hemophilia Activities List (HAL)

HAL contains 7 domains: Lying/sitting/kneeling/standing, functions of the legs, functions of the arms, use of transportation, self-care, household tasks and leisure activities and sports. Additionally, three component scores can be calculated (upper extremity activities, basic lower extremity activities and complex lower extremity activities) as well as an overall score. Normalized score will be calculated for each of the 7 domains, 3 component scores and total score. For detailed scoring method, please see [Appendix IV](#).

Descriptive analyses for normalized score and change from baseline normalized scores for HAL will be provided by study part for each of the dimensions by study part, dose level and visit.

The one sample Wilcoxon signed rank test for a single group data will be used to compare the baseline HAL result vs the last post-baseline assessment at the final treatment dose HAL result, independently for each dose level in Part 2. A 95% Confidence interval for the median change from baseline value at the last post-baseline assessment at the final treatment dose will also be obtained. Sample SAS code can be found in Appendix I.

Statistical Analysis Plan

Catalyst Biosciences, Inc. Protocol # MAA-201

Version 2.0

Syneos Health #1009647

## 9. ANALYSIS OF PHARMACOKINETICS

PK analysis will be performed using non-compartmental analysis in professional PK software Phoenix WinNonLin 6.4 or higher (Certara, Princeton, NJ, USA). The PK TLFs will be produced using SAS statistical package version 9.3 or higher. PK analysis will be performed for PK population as defined in the Section 5.6 of the SAP.

### 9.1 PK SAMPLING SCHEDULE

PK sampling schedule will be specific to each part and dose administration. The PK data will be measured as MarzAA antigen concentration and activity levels. Additional PK data will include FVII, FVIIa activity.

Part 1a - single IV dose of 18 µg/kg MarzAA. PK sampling - predose, and post-dose at 5 and 30 minutes and Hour 1, 3, 6, 9, 12, and 24.

Part 1 b - single SC dose of 30 µg/kg MarzAA. PK sampling - pre-dose and Hour 3, 5, 7, 9, 12, 24, 30, and 48 post-dose.

Part 2 - daily SC dosing with variable dose to be determined.

PK sampling - Day 1 (Pre-dose and Post-dose Hour 7), Day 3 (Pre-dose), Day 5 (Pre-dose), Day 7 (Pre-dose). In the absence of spontaneous bleeding for the first dose level in Part 2 of the study, trough antigen and activity will be measured on days 14, 21, 28, and 50.

In case of spontaneous bleeding the PK samples will be taken within 6 hours of the spontaneous bleed and a pre- and 7 hours post-dose on Day 7, 14, 21, 28, and 50 after dose escalation.

### 9.2 PLASMA PK ENDPOINT

PK parameters will be derived by non-compartmental analysis using intravascular or extravascular trapezoidal log-linear rule for MarzAA antigen concentration and activity and for FVII concentration and FVIIa activity where possible.

**Following PK parameters will be derived for Parts 1a and 1b of the study:**

$C_{max}$ ,  $T_{max}$ ,  $AUC_t$ ,  $AUC_{inf}$  (MarzAA only), MRT (MarzAA only),  $V_z$  (MarzAA only) and CL (MarzAA only) for intravenous injection,  $V_z/F$  (MarzAA only) and CL/F (MarzAA only) for subcutaneous injection, F (MarzAA only) - absolute bioavailability for the subcutaneous injection relative to intravenous bioavailability and other parameters are relevant.

The PK parameters will be estimated as follows:

**Statistical Analysis Plan**

Catalyst Biosciences, Inc. Protocol # MAA-201

**Version 2.0**

**Syneos Health #1009647**

The apparent  $C_{max}$  and the corresponding  $T_{max}$  will be read directly from the concentration-time plot (observed data, not predicted data by the program);

AUCs will be calculated using the linear-log trapezoidal rule:

The terminal elimination rate constant ( $\lambda_z$ ) if data allow will be determined by log linear regression obtained on at least the 3 last quantifiable concentrations and will not include  $C_{max}$ . The adjusted square of the correlation coefficient (R-square adjusted) for the goodness of fit of the regression line through the data points must be at least 0.85 for the  $\lambda_z$  value to be considered acceptable;

$t_{1/2}$  is calculated by the program as  $\ln(2)/\lambda_z$ ;

If the time interval between the lower and upper time points used for the regression spans less than the derived half-life itself, then  $\lambda_z$  and the associated  $t_{1/2}$  will be considered unreliable;

The AUC from 0 to infinity is calculated by the program as:

$AUC_{inf} = AUC_{last} + AUC_{last-inf}$  where last is the sampling time point of the last measurable concentration ( $t_{last}$ ).  $AUC_{last-inf}$  is calculated by the program as:  $C_{last}/\lambda_z$ , where  $C_{last}$  is the observed concentration at time  $t_{last}$  and  $\lambda_z$  is the elimination rate constant during the apparent terminal elimination phase;  $AUC_{inf}$  will only be presented for subjects with a reliable  $\lambda_z$ ;

The AUC extrapolation to infinity must be  $\leq 25\%$  of the total area for  $AUC_{inf}$  to be considered reliable;

CL and CL/F is calculated by program as  $(dose/AUC_{inf})$

$V_z$  and  $V_z/F$  is calculated by the program as  $(dose/AUC_{inf})/\lambda_z$ .

For subjects with unreliable  $\lambda_z$  (i.e., R-square adjusted  $< 0.85$ , interval for  $\lambda_z$  calculation shorter than  $t_{1/2}$ , number of points to calculate  $\lambda_z < 3$ ),  $\lambda_z$ ,  $t_{1/2}$ ,  $AUC_{inf}$ , CL or CL/F and  $V_z$  or  $V_z/F$  will be flagged in the individual data.

For subjects with unreliable  $AUC_{inf}$  (because of extrapolation  $> 25\%$ ),  $AUC_{inf}$ , CL or CL/F and  $V_z$  or  $V_z/F$  will be flagged in the individual data.

Flagged PK parameters will be excluded from summarization and statistical analyses.

Absolute bioavailability F for MarZAA antigen concentration and activity for SC injection vs intravascular route will be calculated using the formula:

$$F = \frac{AUC_{inf}^{SC} \times Dose^{IV}}{AUC_{inf}^{IV} \times Dose^{SC}}$$

Where  $Dose^{IV}$  and  $Dose^{SC}$  are respective doses for both route of administration

Statistical Analysis Plan

Catalyst Biosciences, Inc. Protocol # MAA-201

Version 2.0

Syneos Health #1009647

**Following PK parameters will be derived for Part 2 of the study:**

$C_{min}$  (trough concentrations) and expected  $C_{max}$  (at 7 hrs post-dose), accumulation ratio  $R_{Cmax}$  estimated for all days with PK sampling vs Day 1 where possible. For  $C_{min}$  the ratio  $R_{Cmin}$  will be estimated for each PK sampling day trough concentrations relative to Day 3.

### 9.3 PRESENTATION OF CONCENTRATION DATA

#### 9.3.1 Handling of missing data

Missing concentration and activity data for all subjects who are administered scheduled study treatments will be considered as non-informative missing and will not be imputed. No concentration estimates will be provided for missing sample values.

For the derivation of PK parameters, the following rules will apply:

Concentration values below the assay's lower limit of quantification (BLQ) in pre-dose samples and in samples taken before the time of the first quantifiable concentration will be treated as zero;

The sampling time of pre-dose samples relative to dosing will also be treated as zero;

Post-dose BLQ values after the first quantifiable time point will be set to missing.

If the actual time of sampling is missing, the planned time may be used.

Samples taken outside the sampling windows may be excluded from by-time point summary statistics; this will be determined prior to database lock.

For PK concentration and activity summary, individual concentration versus time curves and mean concentration versus time graphs, the following rules will apply:

PK concentrations BLQ in pre-dose samples and in samples taken before the time of the first quantifiable value will be set to zero;

The PK concentrations BLQ after quantifiable concentration will be set to zero.

No further imputation will be applied to any missing values.

#### 9.3.2 Listing and Presentation of individual PK data

The actual sampling time of PK blood sample collection will be listed for each subject in both parts of the study and will include the deviation in time from the protocol scheduled time, if applicable. Both MarZAA antigen concentration and activity as well as FVII, FVIIa activity will be presented. Subjects with protocol deviations affecting PK may be flagged and excluded from summaries.

**Statistical Analysis Plan**

Catalyst Biosciences, Inc. Protocol # MAA-201

**Version 2.0**

**Syneos Health #1009647**

Individual PK concentrations and activity data for MarzAA antigen concentration and activity levels, FVII, FVIIa activity will be listed by subject, time point and treatment (in relevant concentration units) separately for Parts 1 and 2. For Part 2 the time from start of 1st dose level and time elapsed from dose escalation as well as actual dose used will be presented in the listing of antigen concentration and activity.

The PK concentration and activity data for MarzAA antigen concentration and activity levels, FVII, FVIIa activity will be summarized at each time point by actual treatment. For the Part 2 of the study this summary will be grouped by actual dose level administered taking into account dose escalation history.

Individual subject intense PK parameters for Parts 1a and 1b will be listed for the PK population and will be summarized by treatment. Trough and  $C_{max}$  PK parameters such as  $C_{min}$  for MarzAA antigen concentration and activity levels, FVII, FVIIa activity will be listed for Part 2 PK population. Unreliable PK parameters will be listed but flagged and excluded from summary.

PK parameters of secondary interest for MarzAA antigen concentration and activity levels only, namely R-square adjusted, the number of data points used for estimating  $\lambda_z$ , the upper and lower time point used for estimation of  $\lambda_z$ , and the % AUC extrapolation from  $t_{last}$  to infinity in Parts 1a and 1b of the study will be listed by subject and treatment to enable verification of the exclusions, if any, of data from the summary statistics of the PK parameters of primary interest.

**The following figures will be produced for MarzAA:**

Individual intense PK concentration-time profiles for MarzAA antigen concentration and activity levels, FVII, FVIIa activity will be presented for Parts 1a and 1b separately with all subjects within the same treatment in the same figure on linear and log-linear scales. The profiles can be stratified by subject ID in blocks of 6 to reduce number of curves per plot.

Mean  $\pm$  SD intense PK concentration-time profiles for MarzAA antigen concentration and activity levels, FVII, FVIIa activity for Parts 1a and 1b will be presented combining the curves for both IV and SC treatments within the same figure, on linear and log-linear scales. Box plots comparison of PK parameters  $C_{max}$ ,  $AUC_t$ ,  $AUC_{inf}$  between IV and SC routes.

For Part 2 individual trough and max concentrations for MarzAA antigen concentration and activity levels, FVII, FVIIa activity for all subjects vs dose day of treatment will be presented combined for all subjects within the same dose level. For the subjects requiring dose escalation the individual plots will be produced taking into account the day of the dose escalation.

Mean  $\pm$  SD trough and max PK concentration-time profiles for MarzAA antigen concentration and activity levels, FVII, FVIIa activity will be presented for all subjects,

**Statistical Analysis Plan**

Catalyst Biosciences, Inc. Protocol # MAA-201

Version 2.0

Syneos Health #1009647

combining the curves for different dose levels relative to the day of dose initiation or escalation within the same figure, on linear and log-linear scales

**9.3.3 Summary of PK concentrations and parameters in plasma**

The PK concentrations and activities for MarZAA antigen concentration and activity levels, FVII, FVIIa activity for Part 1 will be summarized by the treatment IV or SC administration of MarZAA.

For Part 2 the summary of results for MarZAA antigen concentration and activity levels, FVII, FVIIa activity will be based on actual dose administered and will be presented relative to the start of dosing for the 1st dose level or day of dose escalation for all subsequent dose levels. The history of dose escalation i.e. the day of bleeding which required dose escalation will be taken into account for the summaries.

PK parameters and concentrations will be summarized by treatment and time point using the following descriptive statistics:

Variable	Summarized with:
PK concentration and activities at each nominal time point	n, number and % BLQ, arithmetic mean, SD, coefficient of variance (CV) %, minimum, median and maximum
AUC, C max , CL or CL/F and Vz or Vz/F, R Cmin , R Cmax , etc.	n, arithmetic mean, SD, CV%, minimum, median, maximum, geometric mean and geometric CV%
t 1/2 , and λ z	n, arithmetic mean, SD, CV%, minimum, median, maximum
T max , T last (actual time)	n, minimum, Q1, median, Q3 and maximum

Note: CV% = SD/mean in %.

%BLQ = 100 \* (total number of subjects who have BLQ values/total number of subjects within each treatment at each time point)

Mean concentrations will not be presented if 70% or more of the actual values for PK population at any one time point in the terminal phase are BLQ or missing.

Samples taken outside the allowed time windows may be excluded from summarization. This will be determined prior to database lock.

The following conventions will be used for the presentation of the descriptive statistics of PK parameters and concentrations:

**PK Reporting Precision**

Statistics	Degree of Precision
------------	---------------------

**Statistical Analysis Plan**

Catalyst Biosciences, Inc. Protocol # MAA-201

Version 2.0

Syneos Health #1009647

Minimum, Maximum; Q1 (25%) and Q3 (75%)	3 significant digits or as needed based on actual measured values (for example PK concentrations)
Mean (arithmetic and geometric), Median	4 significant digits or as needed based on actual measured values (for example PK concentrations)
Standard deviation	5 significant digits or as needed based on actual measured values (for example PK concentrations)
CV% and Geometric CV%	1 decimal point or as needed based on actual measured values (for example PK concentrations)

Additionally, the following inferential analyses will be performed as described below in Sections 9.4 and 9.5 of the SAP:

- Attainment of steady state by MarZAA
- Evaluation of dose effect on dose normalized PK parameters for MarZAA

**9.4 ATTAINMENT OF STEADY STATE FOR FOR MARZAA ANTIGEN CONCENTRATION AND ACTIVITY LEVELS, FVII, FVIIA ACTIVITY**

Attainment of steady state will be estimated for Part 2 data using aggregate assessment of trough concentrations if sufficient data will be available.

To assess whether steady state was achieved for for MarZAA antigen concentration and activity levels, FVII, FVIIa activity after multiple doses of MarZAA, the PK parameters will be summarized for each dosing interval. Aggregate assessment of trough concentrations by will be used to evaluate attainment of steady state. The approach is based on the comparison of log-transformed normalized trough concentration values for each dose to the mean of the results for all the following doses.

The above analysis will be done using repeated measures analysis only if the data are sufficient to support. Alternatively, Analysis of variance (ANOVA) comparison will be carried out on log-transformed  $C_{min}$  (concentrations at the end of dosing interval) for Days 3, 5, 7, 14, 21, 28 and 50 for dosing level 1 (30 µg/mL). If data allow the same analysis may be repeated separately for dose levels 2 (60 µg/mL), 3 (90µg/mL) and 4(120µg/mL) using time relative to dose escalation day. The following example SAS code may be used to conduct the analysis:

```
PROC MIXED;
CLASS time patient;
```

**Statistical Analysis Plan**

Catalyst Biosciences, Inc. Protocol # MAA-201

**Version 2.0**

**Syneos Health #1009647**

MODEL loge(pk) = time / DDFM = KR;

LSMEANS time;

RUN;

The DDFM = KR (KenwardRoger) option performs the degrees-of-freedom calculations detailed by Kenward and Roger (1997).

Contrasts will be tested between a time point and the pooled mean over all remaining time points. For example, following contrasts will be tested as an example for dose level 1 without bleeding and thus without dose escalation:

- Day 3 vs Days 5, 7, 14, 21, 28 and 50
- Day 5 vs Days 7, 14, 21, 28 and 50
- etc.

The first non-significant comparison will be concluded to be the dosing interval at which steady state concentrations are attained. The p-value for difference of Least Square Means (LSM), Geometric Mean Ratio, and the 95% confidence interval for the contrasts will be provided.

The comparison will be also presented graphically as individual and mean plots for trough concentrations at the end of dosing intervals as described in the Section 9.3.2 of the SAP.

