## 8. EFFICACY

Efficacy analyses will be based on the ITT, modified ITT and per-protocol population and summarized by study part, final dose level and overall.

The primary efficacy endpoint will be tested inferentially using a one-sided test with 2.5% significance level. All other statistical tests will be performed at the 0.05 significance level using two-sided tests (i.e. two-sided 95% CIs).

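### The example steady-state code in SAP 9.4 leaves out the subject term that its repeated-measures text implies; run as written, it leans toward declaring steady state too early

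*SAP*

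**What the plan says.** SAP section 9.4 sets out the attainment-of-steady-state analysis on log-transformed troughs. On the method it says: "The above analysis will be done using repeated measures analysis only if the data are sufficient to support". Otherwise an ANOVA is run on the troughs "for Days 3, 5, 7, 14, 21, 28 and 50 for dosing level 1", with the higher dose levels handled in the same way if data allow.

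The code is introduced with "The following example SAS code may be used to conduct the analysis". It consists of the PROC MIXED call, "CLASS time patient", "MODEL loge(pk) = time / DDFM = KR", an LSMEANS statement for time, and RUN. Patient appears in CLASS and nowhere else.

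The contrasts set each day against the pooled later days, beginning with "Day 3 vs Days 5, 7, 14, 21, 28 and 50". The decision rule is: "The first non-significant comparison will be concluded to be the dosing interval at which steady state concentrations are attained". Geometric mean ratios, 95% confidence intervals and trough plots are also promised.

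Section 9.5 (dose proportionality), by contrast, does state the dependence: visit is the repeated measurement and subject a random effect.

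**The concern.** The same subjects supply the troughs on both sides of every contrast, so a subject's general level should cancel. A model with time as its only effect and independent errors does not let it cancel: differences between subjects go into the residual and widen the error of comparisons made within subjects. The Kenward-Roger option cannot repair this, because the residual variance is the only covariance parameter in the model.

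In most tests an oversized standard error is conservative. Here non-significance is the finding, so an oversized standard error moves the declared day forward. At stake are the reported day of steady state and the confidence intervals of the trough ratios.

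**Working it through.** **Inputs from the documents.** Seven troughs per subject at dose level 1 and the Day 3 contrast (SAP 9.4); 12 subjects (SAP 3.3); two-sided 0.05, from the general rule in SAP section 8, "All other statistical tests will be performed at the 0.05 significance level using two-sided tests", which agrees with the 95% intervals in 9.4. The plan gives no standard error, power, variance or correlation for this analysis, so it has no figure to reproduce.

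**Assumptions, not in the documents.** ICC 0.3 to 0.8; total CV 50%; Day 3, 5 and 7 troughs at 70%, 90% and 100% of plateau.

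**Step 1: standard-error ratio.** Write log trough = day mean + subject effect (variance τ²) + error (variance σ²), with ICC = τ²/(τ²+σ²). The contrast coefficients sum to zero, so the subject effect drops out.

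- True variance of the Day 3 contrast: σ²(1+1/6)/n.
- Variance the code estimates: (τ²+σ²)(1+1/6)/n.
- Ratio of standard errors: √((τ²+σ²)/σ²) = 1/√(1−ICC).

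This gives 1/√0.7 = 1.20, 1/√0.5 = 1.41, 1/√0.3 = 1.83 and 1/√0.2 = 2.24. With subjects leaving dose level 1 over time (12, 12, 12, 10, 9, 8, 7 per visit) the ratios are 1.18, 1.40, 1.80 and 2.20. If correlation decays by visit (AR(1)), the Day 3 ratio is only 1.02, 1.05, 1.15 and 1.29. The last contrast, Day 28 against Day 50, keeps the full ratio because those visits are adjacent.

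**Step 2: hand check at ICC 0.5, n = 12.** Total log variance is ln(1+0.5²) = 0.223.

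- Standard error from the code: √(0.223 × (7/6)/12) = 0.147. True standard error: 0.147 × √0.5 = 0.104.
- True difference: ln 0.7 − (ln 0.9)/6 = −0.357 + 0.018 = −0.339.
- Significance limit with the code (84−7 = 77 df): 1.991 × 0.147 = 0.293. With a subject term (11×6 = 66 df): 1.997 × 0.104 = 0.208.
- Chance of a non-significant result: Φ((0.293−0.339)/0.104) = Φ(−0.44) ≈ 33% with the code, and Φ((0.208−0.339)/0.104) = Φ(−1.26) ≈ 10% with the subject term.

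**Step 3: simulation of the rule** (20,000 trials per setting, compound symmetry; repeat runs differ by about a percentage point). Share of trials that wrongly place steady state at Day 3:

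| Subjects | ICC | Code as written | With subject term |
|---|---|---|---|
| 12 | 0.3 | 36% | 23% |
| 12 | 0.5 | 33% | 10% |
| 12 | 0.7 | 29% | 1.5% |
| 12 | 0.8 | 27% | 0.1% |
| 6 | 0.5 | 68% | 40% |

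When troughs are truly flat from Day 3, the nominal 5% test rejects in 2.2%, 0.8%, 0.2% and 0.01% of trials with the code (12 subjects, ICC 0.3, 0.5, 0.7 and 0.8), and in about 5% with a subject term.

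**Why six subjects matters.** A spontaneous bleed after the fifth dose moves a subject off dose level 1. At the planning ABR of 6, if every bleed were spontaneous and Poisson, the share reaching Day 50 without one is exp(−6×45/365) = 0.48, or about 6 of 12.

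**The case against.** The code is offered as an example that may be used, and the text puts repeated measures first. The snippet is plainly schematic: it writes a log function inside the MODEL statement and has no CONTRAST or ESTIMATE statement for the listed contrasts. Requesting Kenward-Roger and declaring patient both suggest that a line was dropped by accident, and SAP section 17 has programs checked for logic. A reader might infer that the SAP commits to analysing troughs as independent. The documents do not support that. What stands is that neither the text nor the code of 9.4 names a subject effect or covariance structure, and that the fallback ANOVA is silent on it.

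The size is also open. A reader could pick a between-subject CV of 50% and a within-subject CV of 25% and find Day 3 wrongly accepted in about 37% of trials against 0.4%. That choice implies an ICC of 0.223/(0.223+0.061) = 0.79 and keeps all 12 subjects on dose level 1; the documents support neither. With an ICC near zero or fast-decaying correlation, the effect on the Day 3 contrast is small.

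The consequence is limited. The analysis is conditional on sufficient data, dose escalation is triggered by spontaneous bleeding and not by this test, and the ratios and plots would show a low Day 3 trough whatever the p-value. All of this stands, and it bears on importance, not on whether the code is right.

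**Conclusion.** The point holds as a mismatch between code and text within SAP 9.4, with a fallback that is under-specified in the same way. Used as printed, the code gives contrast standard errors and intervals that are too wide whenever within-subject correlation is positive, and the decision rule turns that into a lean toward an early day. The direction follows from the design. The magnitude rests on the assumed ICC, CV and trough profile: at 12 subjects, wrong acceptance of Day 3 goes from a modest excess at ICC 0.3 to a large one at 0.7 and above.

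It would be wrong to conclude that the subject term makes the rule sound. With 6 subjects at ICC 0.5 the rule still errs in 40% of trials, because it reads non-significance in a small sample as attainment. The primary endpoint is not affected.

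**What to change.** In the SAP 9.4 code, add `RANDOM patient;` or `REPEATED time / SUBJECT=patient` with a named covariance structure and a fallback if it does not converge. Compound symmetry is a workable default; an unstructured matrix for seven visits has 7×8/2 = 28 parameters, too many for 6 to 12 subjects. State that the ANOVA alternative also carries the subject term, in line with section 9.5. While editing, add ESTIMATE statements for the listed contrasts and take the log in a prior data step.

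A sentence saying that the declared day will be read together with the geometric mean ratio and its interval, already promised, would acknowledge the remaining weakness of the rule. The cost is a few lines in the SAP, with no new data and no protocol change.
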